Assessing the Relative Efficacy of Communication Modalities for Messages Promoting Flu
Shots

Study Protocol with SAP

NCT05509270

10/6/2022

Study Protocol

Scientific Background

The Centers for Disease Control (CDC) recommends a flu vaccination to everyone aged 6+ months, with rare exception; almost anyone can benefit from the vaccine, which can reduce illnesses, missed work, hospitalizations, and death. Flu shots are particularly important for patients at high risk of experiencing severe outcomes.

During the 2020-21 and 2021-22 flu seasons, the study team sent messages to Geisinger patients in the top 10% of risk for flu and complications according to an artificial intelligence algorithm. Messages that told patients they were at high risk significantly increased their likelihood of getting vaccinated.

Objectives

The present study extends previous work by testing which modality or modalities are most effective at boosting flu shot rates in patients at high risk. In previous campaigns, patients received messages via all communication modalities patients were eligible for (mailed letter, SMS text, and/or patient portal message). In this study, patients were randomized to receive high-risk messages in one or more modalities.

Design

This study is a randomized controlled trial with up to 6 study arms, depending on modality eligibility. Patients were randomized to receive high-risk messages in one or more modalities they were eligible for.

Methods

The sample included 43,225 patients. Patients were first divided into the following *modality groups* according to the modalities they were eligible for:

- A. Letter + Patient portal + SMS (29,505 patients)
- B. Letter + Patient portal (4,980 patients)
- C. Letter only (4,366 patients)
- D. Letter + SMS (4,364 patients)
- E. Patient portal + SMS (8 patients)
- F. SMS only (2 patients)

Note: there were no eligible patients who had Patient portal access only.

Then, each modality group was randomized across *study arms* the patients were eligible for:

- 1. Control (no message)
- 2. Letter only
- 3. Patient portal only
- 4. SMS only
- 5. Patient portal + SMS

6. Letter + Patient portal + SMS

For example, patients who are eligible to receive a letter and an SMS (*modality group D*) were randomized to Control (*study arm 1*), Letter only (*study arm 2*), or SMS only (*study arm 4*).

Note: Due to power limitations, we did not test all possible combinations of modalities (e.g., we did not include a Letter + SMS study arm).

Power Analysis

Our primary analysis sample includes patients in *modality group A*, with patients eligible for all three modalities. This group includes between 4,916 and 4,919 patients per arm. This sample size allows 80% power to detect an increase in flu vaccination rates from 35% to 37.7% with alpha = .05.

Project Status

All intervention messages have been sent. Letters were sent on 9/6/22. Patient portal messages and SMS were sent on 9/8/22, to match the date when the majority of patients were expected to receive the letter (i.e., 2 days after the letters are sent). The primary outcome date was 10/4/22.

As of this writing, the study team has not yet obtained or analyzed any outcome data from the study.

Statistical Analysis Plan

Analysis Exclusion Criteria

We will remove patients from analysis who received a flu shot prior to 9/6/22, the study start date, because they could not have been influenced by our nudge messages to get a flu shot.

Planned Analyses

Primary Outcome: Flu vaccination within 4 weeks of the first message send date [Time Frame: 4 weeks after the first messages are sent in the study]

The primary analysis sample will be patients in modality group A, who are eligible for all 3 modalities and were randomized across all study arms. We will address the following four questions in this primary analysis sample:

Question 1: Are flu shot rates higher when a high-risk flu shot message is sent in any modality or combination of modalities independently compared to when no message is sent?

Hypotheses:

- 1.a. Flu shot rates will be higher in the Letter only arm than the Control arm
- 1.b. Flu shot rates will be higher in the Patient portal only arm than the Control arm
- 1.c. Flu shot rates will be higher in the SMS only arm than the Control arm
- 1.d. Flu shot rates will be higher in the Patient portal +SMS arm than the Control arm
- 1.e. Flu shot rates will be higher in the Letter + Patient portal + SMS arm than the Control arm

Analysis 1 (Confirmatory): We will run an OLS regression with a categorical independent variable coding for study arm with the Control arm coded as baseline. All 5 hypotheses above will be tested within the same regression.

Question 2: Which modality on its own most effectively increases flu shots?

Analysis 2 (Exploratory): We will run an OLS regression with a categorical independent variable coding for study arm, including only patients randomized to be sent messages in one modality (Letter only, Patient portal only, SMS only). We will test for significant pairwise differences in flu vaccination rates between the study arms by running Tukey's HSD test.

Question 3: Are Patient portal and SMS messages better in combination than either modality alone?

Analysis 3 (Exploratory): We will run an OLS regression including patients in the Patient portal only, SMS only, and Patient portal + SMS arms, with a categorical independent variable coding for study arm. The Patient portal + SMS arm will be coded as baseline, so the individual Patient portal and SMS modalities can be compared directly against the combination of the two modalities.

Question 4: Is there value to sending a letter in addition to Patient portal and SMS messages?

Analysis 4 (Exploratory): We will run an OLS regression comparing the Patient portal + SMS study arm to the Letter + Patient portal + SMS arm, with a categorical independent variable coding for study arm.

Analyses with additional modality groups

We also will run the following **additional analyses on the primary outcome:**

Within *modality groups B* and *D* (Letter + Patient portal, Letter + SMS, respectively), we will run Analyses 1 and 2 (comparing active study arms to the control arm, and comparing active study arms to one another).

For *modality group C* (Letter only), we will run Analysis 1, comparing the letter arm to control.

Because there are so few patients in *modality groups E* (8 patients) and *F* (2 patients), we will not separately analyze data on these groups.

Finally, we will run Analyses 1 and 2 on the entire sample, with all modality groups combined.

Sensitivity Analyses and Robustness Checks

Recent work suggests that OLS regressions are appropriate in randomized experiments with binary outcome variables such as ours (Gomilla, 2021). However, as a robustness check, we will also run the regressions described above as logistic regressions instead of OLS regressions.

Other Pre-specified Outcomes

Other Pre-specified Outcomes listed below include flu outcomes (diagnosis, complications) and COVID-19 vaccination. If there are any differences in these outcomes as a function of study arm, the mechanism would almost certainly be increased flu vaccination. Therefore, we will only run analyses on Other Pre-specified Outcomes for analyses above where there is a difference in flu vaccination.

1. High confidence flu diagnosis

Patient received a flu diagnosis via a positive polymerase chain reaction (PCR)/antigen/molecular test (yes/no) during the 2022-23 flu season (from the first message send date through April 30, 2023).

[Time Frame: Up to 8 months]

2. "Likely flu" diagnosis

Received a "high confidence flu" diagnosis (with positive PCR/antigen/molecular test) and/or "likely flu" diagnosis (as assessed via International Classification of Disease [ICD] codes or Tamiflu administration or positive PCR/antigen/molecular test) (yes/no) during the 2022-23 flu season (from the first message send date through April 30, 2023).

Note that "likely flu" is a superset of the "high confidence flu" diagnoses.

[Time Frame: Up to 8 months]

3. Flu complications

Diagnosed with flu-related complications (yes/no) from the first message send date through July 31, 2023.

[Time Frame: Up to 11 months]

4. ER visits

Number of ER visits from the first message send date through July 31, 2023.

[Time Frame: Up to 11 months]

5. Hospitalizations

Number of hospitalizations from the first message send date through July 31, 2023.

[Time Frame: Up to 11 months]

6. COVID-19 vaccination rates

Received at least one COVID-19 vaccination (yes/no) during the 2022-23 flu season (from the first message send date through April 30, 2023).

[Time Frame: Up to 8 months]

Additional Exploratory Analyses

1. Age and gender

While older patients tend to be aware of their increased vulnerability, younger patients may be more surprised to learn of their high-risk status. Additionally, our previous work suggests that males and females are differently likely to get vaccinated as a function of age, with younger females *more* likely to get vaccinated than males, and older females *less* likely to get vaccinated than older males.

We will therefore run an OLS regression including binned age (18-24, 35-44, 45-54, 65+), gender, and their interaction.

We will also test for an interaction between age, gender and study arm, as people of different ages and genders may be differentially receptive to different modalities.

2. Timing of shot

We will run regression models to test whether intervention messages influenced the timing (time elapsed since the beginning of the intervention, September 6, 2022) of flu shots.

3. Risk level

As in our studies in the 2020-21 and 2021-22 flu seasons, patients who were in the top 3% of risk were told they were in the top 3% of risk, while those in the next 7% (i.e., the top 4-10% of risk) were told they were in the top 10% of risk. We will test whether flu vaccination rates differ across risk level (top 3%, top 10%) and whether risk level interacts with study arm among patients in *modality group A* who have access to all 3 modalities.

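### No planned analysis compares flu vaccination by arm at season end, so a 4-week difference does not by itself separate added shots from earlier ones

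*Combined protocol and SAP*

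**What the plan says.** - **Aim.** The Objectives section describes "testing which modality or modalities are most effective at boosting flu shot rates in patients at high risk". It attaches no time limit, and neither do Questions 1 and 2 under Planned Analyses.
- **Outcome.** The primary outcome is "Flu vaccination within 4 weeks of the first message send date". Project Status adds "The primary outcome date was 10/4/22", "Letters were sent on 9/6/22" and "Patient portal messages and SMS were sent on 9/8/22". Analyses 1 to 4, the analyses in the other modality groups and the logistic regression checks all use this outcome.
- **Longer follow-up.** Under Other Pre-specified Outcomes, flu diagnoses run through April 30, 2023. Complications, ER visits and hospitalizations run through July 31, 2023. COVID-19 vaccination is defined as "Received at least one COVID-19 vaccination (yes/no) during the 2022-23 flu season (from the first message send date through April 30, 2023". Flu vaccination at season end is not listed.
- **Condition for those outcomes.** The same section gives increased flu vaccination as the almost certain mechanism for any effect on them, and concludes that "we will only run analyses on Other Pre-specified Outcomes for analyses above where there is a difference in flu vaccination".
- **Timing.** Additional Exploratory Analyses, item 2 (Timing of shot), plans regressions of time to flu shot, counted from September 6, 2022. It gives no end date, no model type and no rule for patients who are never vaccinated.

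**The concern.** A reminder sent in early September can act in two ways. It can persuade someone who would otherwise have gone unvaccinated, or it can prompt someone who would have had the shot later to have it sooner. Both raise the proportion vaccinated at 4 weeks. Only the first raises the proportion vaccinated over the season.

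This matters in two places. First, the stated aim and Questions 1 and 2 invite an unqualified conclusion that a modality increases flu shots, and the 4-week outcome supports that only for the 4-week window. Second, the 4-week difference decides whether outcomes running to April and July 2023 are examined. If that difference is partly acceleration, those outcomes would be interpreted against an increase in vaccination that the plan does not quantify at season end.

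**Working it through.** **Inputs from the documents**
- 4,916 to 4,919 patients per arm in group A; 35% versus 37.7%; alpha .05; 80% power (Power Analysis). The time window of the 35% is not stated.
- First messages 9/6/22; portal and SMS messages 9/8/22; primary outcome date 10/4/22 (Project Status).
- Season cutoff April 30, 2023 (Other Pre-specified Outcomes).

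**Assumptions, not in the documents**
- The 35% control rate refers to the 28 days to 10/4/22.
- Season-end uptake S is between 50% and 60%, equal in both arms in the pure-shift case.

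**1. The plan's power figure.** Two-sided, unpooled standard error, n = 4,916:

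SE = √[(0.35 × 0.65 + 0.377 × 0.623) / 4,916] = √(0.46237 / 4,916) = 0.00970

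Power = Φ(0.027 / 0.00970 − 1.96) = Φ(0.82) = 79.5%

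This agrees with the stated 80%.

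**2. Windows.** 9/6/22 to 10/4/22 is 28 days (26 for portal and SMS). 9/6/22 to April 30, 2023 is 236 days. That leaves 236 − 28 = 208 days with no defined flu vaccination outcome.

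**3. How much shifting would produce the powered effect?** If no shots are added, the 2.7 points must come from shots that would have occurred after 10/4/22. The share moved forward is 0.027 / (S − 0.35).
- S = 50%: 0.027 / 0.15 = 18%
- S = 60%: 0.027 / 0.25 = 10.8%

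In either case the primary test has 79.5% power at 4 weeks while the season-end rates are equal.

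If the 4-week control rate were lower than 35%, a smaller share would suffice for the same 2.7 points. At 20% it is 0.027 / 0.30 = 9.0% (S = 50%) or 0.027 / 0.40 = 6.8% (S = 60%). At 10% it is 6.8% or 5.4%.

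**4. What a season-end comparison could show.** With 4,916 per arm and two-sided .05, the increase detectable with 80% power is 2.82 points at a 50% control rate and 2.75 at 60%, against 2.72 at 35%.

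| Part of the 2.7 points that is added shots | Season-end difference | Season-end power (S = 50% to 60%) |
|---|---|---|
| All | 2.7 points | 76% to 79% |
| Half | 1.35 points | 27% to 28% |
| None | 0 | no difference to detect |

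Precision at season end is thus close to that at 4 weeks. A non-significant season-end result would not prove pure acceleration, because a half-added effect would usually be missed. The estimate and its confidence interval should carry the interpretation.

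**The case against.** **The timing analysis already covers this.** It is aimed at acceleration, and it has no stated 10/4/22 cutoff. A reader might infer that flu vaccination is recorded only to 10/4/22, or that the trial is unable to tell added from earlier shots. The documents support neither: the 28-day limit belongs to the primary outcome, and other outcomes are followed well beyond it. What stands is narrower. The analysis is exploratory and lacks a window, a model and a rule for unvaccinated patients. Restricted to vaccinated patients, or to shots by 10/4/22, it could not separate the two effects.

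**Four weeks is a legitimate, explicit choice.** Agreed. It is a valid primary outcome for a short-term claim.

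**A shift of about two days is enough to explain the effect.** A reader might compute 35 / 28 = 1.25 points per day and 2.7 / 1.25 = 2.2 days. That needs the 35% to be a 28-day rate and uptake after 10/4/22 to continue at the same pace. At an assumed slower pace of 0.67 points per day, the same shift yields about 0.67 × 2.16 = 1.4 points. Against 35%, that has power of only Φ(0.014 / 0.00966 − 1.96), about 30%. At half the initial pace, the full effect needs 2.7 / 0.625 = 4.3 days. The two-day figure should not be relied on.

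**Late extra shots would be missed and the flu outcomes wrongly skipped.** This is possible in principle, but nothing in the documents suggests that messages sent in early September would act only after four weeks.

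**Earlier vaccination can itself affect flu outcomes.** It adds protected time within follow-up, so conditioning on the 4-week difference is not without logic. That difference still does not show how many more patients were vaccinated over the season.

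**Rankings may reflect speed.** The plan timed portal and SMS messages to expected letter arrival, which limits differences due to delivery. Differences in speed of response could remain.

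**Conclusion.** The point holds in a limited form. The 4-week primary comparison is valid, and its power figure reproduces. The gap is that no planned analysis compares cumulative flu vaccination by arm at season end, and the one analysis directed at timing is too loosely specified to fill it.

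A 4-week difference alone therefore supports a conclusion about vaccination within 4 weeks, not a net increase over the season. Under the assumptions stated, moving 11% to 18% of later shots forward would reproduce the whole 2.7-point effect with none added. This shows that acceleration is a credible alternative explanation. It does not show that it occurs, and the documents give no season-end rate from which to judge.

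This is an inexpensive improvement that widens what the trial can conclude, not a defect in the primary test.

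**What to change.** 1. Keep vaccination within 4 weeks as the primary outcome.
2. Add a pre-specified secondary outcome: flu vaccination from 9/6/22 through April 30, 2023 (yes/no). Run Analyses 1 to 4 on it in modality group A.
3. Claim a net increase in flu shot rates only where the season-end difference, with its confidence interval, supports it. Otherwise limit the conclusion to vaccination within 4 weeks.
4. Interpret flu diagnoses, complications, ER visits and hospitalizations alongside the season-end vaccination difference.
5. Run the timing analysis over the same window, with a named model and with unvaccinated patients included as censored.
6. State which window the 35% in the Power Analysis refers to.

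The document, dated 10/6/2022, says that no outcome data had been obtained, so an addition made at that point would be truly pre-specified. Vaccination follow-up to April 30, 2023 is already planned for COVID-19, and no patient contact is needed. The costs are one more set of secondary tests and the possibility that some effects look smaller at season end.

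### Exploratory Analysis 2 could use a step-down Tukey rule: same 5% family-wise error, and more power to separate the best single modality from both others (a cheap improvement, not an error)

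*Combined protocol and SAP*

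**What the plan says.** Under Planned Analyses the plan poses "Question 2: Which modality on its own most effectively increases flu shots". Analysis 2, labelled exploratory, fits an OLS regression to the patients assigned to letter only, portal only or SMS only. It then says: "We will test for significant pairwise differences in flu vaccination rates between the study arms by running Tukey's HSD test". No step-down or closed procedure is named and no simultaneous confidence intervals are requested. No alpha is given for the Tukey test; .05 appears only in the Power Analysis.

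The main setting is modality group A: "This group includes between 4,916 and 4,919 patients per arm". The Power Analysis adds: "This sample size allows 80% power to detect an increase in flu vaccination rates from 35% to 37.7% with alpha = .05".

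Analysis 2 is repeated in groups B and D, which have two active arms each. It is then extended further: "Finally, we will run Analyses 1 and 2 on the entire sample, with all modality groups combined". Among the four numbered analyses, only Analysis 1 is labelled confirmatory.

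**The concern.** Single-step Tukey holds all three pairs to the same bar, |t| > 2.344. To name one modality as best, that modality must separate from both others, so two pairs must clear the bar. With three arms this is stricter than family-wise control requires. Once the hypothesis that all three arms are equal has been rejected, at most one pair can still be truly equal, and the pairs can then be tested at the ordinary 1.96.

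What is at stake is how often the trial can answer Question 2. Analysis 2 is the only planned analysis that sets all three single modalities against one another. The messages have been sent and the sample is fixed, so the decision rule is one of the few places left where power can be gained.

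**Working it through.** **Inputs.** From the documents: three single-modality arms; 4,916 to 4,919 patients per arm in group A; 35% and 37.7%; alpha .05. Assumed: alpha .05 also applies to Tukey, and the rates of the three modalities. The documents give no expected gap between modalities, so a range is shown.

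**1. The plan's own power figure.** For one two-sided comparison, SE = √[(0.35×0.65 + 0.377×0.623)/4,916] = 0.00970. Then 0.027/0.00970 = 2.784, and power = Φ(2.784 − 1.960) = 79.5%. The stated 80% reproduces as a single, unadjusted, two-sided comparison.

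**2. The two bars.** Tukey's critical |t| is q(.95; 3, 14,745)/√2 = 3.315/1.414 = 2.344. Near a rate of 36%, SE = √(2×0.36×0.64/4,916) = 0.00968. Tukey therefore needs a gap of 2.344×0.968 = 2.27 points for every pair. The step-down rule needs that for the pair with the largest |t|, and 1.960×0.968 = 1.90 points for the others.

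**3. Why error stays at 5%.** Among three arms, any two true pairwise equalities imply the third. The closed family is therefore the hypothesis that all three are equal, plus the three single-pair hypotheses. Testing the first by max |t| > 2.344 and each pair by |t| > 1.96 puts each at 5%, to large-sample approximation and with a common variance. Closed testing then controls family-wise error strongly.

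**4. Why nothing is lost against Tukey.** A pair with |t| > 2.344 opens the gate and also exceeds 1.96. In simulation, no replicate had a pair that Tukey declared and step-down did not.

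**5. Size.** Binomial arms, 4,916 per arm, pooled OLS variance, 400,000 replicates per row. Runs at 4,917 agree.

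| Assumed rates (%) | Best beats both: Tukey | Best beats both: step-down | At least one difference: both rules |
|---|---|---|---|
| 35 / 35 / 36 | 3.1% | 6.3% | 17.1% |
| 35 / 35 / 36.5 | 9.8% | 17.1% | 33.6% |
| 35 / 36.35 / 37.7 | 15.6% | 25.9% | 70.2% |
| 35 / 35 / 37.7 | 52.5% | 66.2% | 82.2% |
| 35 / 37.7 / 40.4 | 66.4% | 78.8% | 99.9% |
| 35 / 35 / 39 | 93.3% | 97.0% | 99.2% |
| 20 / 20 / 22.7 | 72.6% | 83.3% | 92.8% |
| 10 / 10 / 12.7 | 95.1% | 97.9% | 99.4% |

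At 35/35/37.7%, power per truly different pair is 67.3% with Tukey and 74.2% with step-down. Tukey would need about 6,200 per arm, roughly a quarter more, to reach 66% for beating both.

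**6. False declarations.** With all arms at 35%, any rejection occurs in 5.0% to 5.1% of trials under both rules, depending on the run. At 35/37.7/37.7%, the equal pair is declared in 2.0% of trials with Tukey and 5.0% with step-down.

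**7. The gate in the whole sample.** All of groups A to D feed the letter arm, so arm sizes differ. Assuming equal allocation within each group (not stated for B to D) and leaving out the ten patients in E and F:

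- Letter: 29,505/6 + 4,980/3 + 4,366/2 + 4,364/3 ≈ 10,215
- Portal: 29,505/6 + 4,980/3 ≈ 6,577
- SMS: 29,505/6 + 4,364/3 ≈ 6,372

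Near 36%, the Tukey-Kramer bar is 2.344×0.48×√(1/6,577 + 1/6,372) = 1.98 points for portal against SMS, and 2.344×0.48×√(1/10,215 + 1/6,372) = 1.80 points for letter against SMS. Suppose the observed gaps were 1.90 and 1.85 points. A gate on the largest raw difference would stay shut, although Tukey-Kramer declares letter against SMS. This happened in up to about 0.5% of simulated trials; a gate on the largest |t| lost none. The gate must therefore use |t|.

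**The case against.** Tukey's HSD is valid and standard for all pairwise comparisons, and Analysis 2 is exploratory, so no confirmatory conclusion depends on it. All of this stands.

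The extra power is not free. Step-down spends error that Tukey leaves unused: when one pair is truly equal, the chance of declaring it different rises from about 2% to at most 5%. This touches Question 2 directly, because if two modalities tie for best, that is how often the tie is wrongly broken. Both figures are within the 5% family-wise level, so the guarantee is the same, but Tukey is the more protective rule in that configuration. Tukey also has intervals that match its tests. Under step-down, a pair with |t| between 1.96 and 2.344 is declared different beside a Tukey interval that includes zero. These points stand as costs to be disclosed.

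The size depends on assumed gaps. The 35% to 37.7% in the Power Analysis is a generic increase, most naturally message against no message. At gaps of 1 to 1.5 points, naming a best arm is unlikely under either rule.

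A reader might infer from the 67% per-pair power under Tukey that the stated 80% is wrong. The documents do not support that. The power statement mentions neither Analysis 2 nor Tukey, and it reproduces for the single comparison it describes.

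**Conclusion.** A cheap improvement, not an error. For the three single-modality arms, the step-down rule controls family-wise error at the same 5%, never declares less than Tukey, and raises the chance of separating the best modality from both others. The gain is about 14 points (52% to 66%) at 35/35/37.7%, about 7 points (10% to 17%) at 35/35/36.5%, and between 3 and 14 points over the scenarios shown. It fades once the gap is so large that both rules nearly always succeed. Only the second and third pairs benefit; the chance of at least one difference is unchanged.

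This rests on assumed between-modality rates, alpha .05 for Tukey, and group sizes before patients vaccinated ahead of 9/6/22 are removed, which would lower power slightly under both rules. It does not reach groups B and D, where a single active pair is tested and Tukey reduces to the ordinary t-test. The stronger reading, that the planned test is invalid or leaves the trial's main conclusions unsafe, has no support: the confirmatory Analysis 1 is untouched.

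**What to change.** Replace the Tukey sentence in Analysis 2 with:

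> In group A and in the whole sample, if the maximum of the three pairwise |t| statistics (Tukey-Kramer when arm sizes differ) does not exceed Tukey's critical value (2.344), no pair is declared different. If it does, every pair with |t| > 1.96 is declared different. Tukey simultaneous 95% intervals are reported alongside.

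Groups B and D need no change, and neither does the existing power statement.

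The SAP should state three costs. A declared pair may have a Tukey interval that includes zero. The false-declaration rate for a single equal pair rises from about 2% to at most 5%. More comparisons may carry forward to the Other Pre-specified Outcomes, which are analysed only where flu vaccination differs. The plan does not say whether that condition applies per analysis or per pair. Applied per analysis, the new rule changes nothing, because the chance of at least one difference is the same; applied per pair, more pairs can qualify. One line should settle which is meant.

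The effort is a few lines of SAP text. The Project Status section says that no outcome data had been obtained or analysed at the time of writing; the change should be made and dated while that remains true.

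### Single-modality effects are tested separately in each modality group, but no analysis tests whether they differ between groups, and low power makes mixed significance likely even if effects are identical

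*Combined protocol and SAP*

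**What the plan says.** Under Methods, patients are divided by the modalities they can receive and randomized within those groups. Group A (all three modalities) has 29,505 patients, B (letter and portal) 4,980, C (letter only) 4,366 and D (letter and SMS) 4,364. Groups E and F have 10 patients together and are not analysed separately.

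Group A is the primary analysis sample. Under Analyses with additional modality groups, the plan says of B and D: "we will run Analyses 1 and 2 (comparing active study arms to the control arm, and comparing active study arms to one another". Of C it says: "we will run Analysis 1, comparing the letter arm to control". Analyses 1 and 2 are then run once more on all groups combined, with no mention of a modality-group term.

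Power is given for group A only: "This group includes between 4,916 and 4,919 patients per arm", and "This sample size allows 80% power to detect an increase in flu vaccination rates from 35% to 37.7% with alpha = .05".

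The interactions named under Additional Exploratory Analyses are age and gender with arm, and risk level with arm (the latter in group A). None involves modality group.

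**The concern.** Each group-specific contrast gets its own p-value, and readers will set those p-values side by side. A significant letter effect in A beside a non-significant one in C looks like evidence that letters work for patients with digital access but not for those without. A difference in significance is not evidence of a difference in effect. The plan offers no direct comparison and no rule for reading discordant results.

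What is at stake is the advice given about patients who cannot be reached by every channel. There may be a knock-on effect too. The Other Pre-specified Outcomes are analysed only where flu vaccination differs. If that means statistical significance, which the plan does not say, low power in B, C or D would also decide whether those outcomes are examined there.

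**Working it through.** **Inputs.** From the documents: the group totals above, 4,916 to 4,919 per arm in A, 35% against 37.7%, and alpha .05. Group D's three arms are given in the Methods example; B is taken to have three by the same logic (Control, Letter, Portal), and C two. Assumed: equal allocation within B, C and D, a 35% control rate in every group, two-sided tests, and no allowance for the planned removal of patients vaccinated before 9/6/22.

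**Patients per arm.** A: 29,505/6 = 4,917.5. B: 4,980/3 = 1,660. C: 4,366/2 = 2,183. D: 4,364/3 = 1,455.

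**Formula.** Power = Φ[(d − 1.96·SE0)/SE1], where d = .027, SE0 = √(2 × .3635 × .6365/n) and SE1 = √((.35 × .65 + .377 × .623)/n).

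**The plan's own figure.** In A, SE0 and SE1 are both .00970, so power = Φ[(.027 − .01901)/.00970] = Φ(.824) = 79.5%. The stated 80% is reproduced. A one-sided test would give 87.3%, so two-sided is the natural reading.

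**Letter against Control, same effect in every group**

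| Group | n per arm | SE0 | Power | Detectable at 80% power |
|---|---|---|---|---|
| A | 4,917.5 | .00970 | 79.5% | 2.7 points |
| B | 1,660 | .01670 | 36.6% | 4.7 points |
| C | 2,183 | .01456 | 45.8% | 4.1 points |
| D | 1,455 | .01784 | 32.8% | 5.0 points |

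**Joint results** (the groups are independent):
- All four significant: .795 × .366 × .458 × .328 = 4.4%.
- None significant: .205 × .634 × .542 × .672 = 4.7%.
- Mixed: 1 − .044 − .047 = 90.9%. A 200,000-run binomial simulation also gives 90.9%.
- A significant and C not: .795 × .542 = 43%.
- A significant and none of B, C, D: .795 × .231 = 18%.
- Portal (A and B), exactly one significant: .795 × .634 + .205 × .366 = 58%. SMS (A and D): .795 × .672 + .205 × .328 = 60%.

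**Sensitivity of the 91%.** At a 35% control rate, mixed significance is 38% at +1 point, 79% at +2, 90% at +3, 69% at +4, 38% at +5 and 15% at +6. With +2.7 points and control rates of 20% to 40% in B to D, it is 88% to 91%.

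**Role of unequal size.** Four equal groups with the same total have 10,215/4 = 2,554 per arm and power of 51.8% each. Mixed significance is then 1 − .518⁴ − .482⁴ = 87%.

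**The whole-sample run.** Letter and Control each have about 4,917.5 + 1,660 + 2,183 + 1,455 = 10,215 patients over A to D, in the same group mix. Portal and SMS do not match Control in mix: group A supplies 4,917.5/10,215 = 48% of Control, but 4,917.5/6,577.5 = 75% of Portal only and 4,917.5/6,372 = 77% of SMS only.

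**The proposed analysis.** A group-stratified letter effect over A to D has about 98% power at 35% against 37.7%. With identical effects, the 3-df interaction test declares a difference in 5.0% of simulated trials. From the noncentral chi-square, its power is about 36% if the effect is 2.7 points in A and zero in B, C and D, and about 25% if it is zero only in C.

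**The case against.** The best case for the plan is that these are additional analyses on a secondary question. Group A is the declared primary sample, no hypothesis concerns differences between modality groups, and nothing says that groups will be compared by their p-values. The planned whole-sample run also means that the letter evidence does not rest on four isolated tests; for that contrast, equal allocation balances the group mix. All of this stands. It limits the importance of the point, but a whole-sample run estimates an overall effect and cannot say whether effects differ.

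A reader might take the figures further than they go, in four ways:

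- The 91% is not the chance of opposing results, nor of one particular misreading. It counts every pattern that is neither all significant nor all non-significant. The contrast between A and letter-only C arises about 43% of the time. The 91% is also near the peak of its curve, and 2.7 points is the power assumption for A, not a forecast for B to D.
- Unequal group size is not the main cause, since four equal groups would still give about 87%.
- It does not follow that B, C and D would all look null. Each is more likely than not to be non-significant, but all three are so only .634 × .542 × .672 = 23% of the time.
- The documents do not support a charge that the plan itself infers group differences from separate p-values.

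The interaction test is also weak, as its 25% to 36% power shows. That is a reason to rely on estimates and intervals alongside it, not to leave the comparison out.

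**Conclusion.** The gap is real: single-modality effects are tested group by group, and no planned analysis asks whether they differ. At the planned effect, with equal allocation and a 35% control rate throughout, identical letter effects would give mixed significance about 91% of the time. The figure ranges from 15% to 91% over effects of 1 to 6 points. The driver is low power within groups combined with the lack of a direct comparison. The plan leaves a misreading open; it does not commit one. The primary analysis in group A is unaffected, so this is a worthwhile improvement to the secondary analyses, not a flaw in the main result.

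**What to change.** For each single-modality contrast, fit one OLS model over the groups that randomized it: Letter over A to D, Portal over A and B, SMS over A and D. Include modality-group terms and report:

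1. the group-stratified effect (for Letter, about 10,215 per arm and about 98% power at the planned effect);
2. the group-by-arm interaction test (3, 1 and 1 degrees of freedom respectively);
3. each group's effect with its 95% interval, in one plot.

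State that groups will be said to differ only on the interaction, not on group-specific p-values. The planned logistic models can serve as the robustness check here too. The group terms also deal with the unequal mix of groups in the Portal and SMS contrasts.

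The cost is a paragraph of SAP text and three regressions. The document reports that no outcome data had been obtained or analysed; if that has changed, the addition should be labelled post hoc. The downside is the low power of the interaction test: the SAP should say that a non-significant result is not proof of equal effects.
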